#### **4.5.4.3 Criteria to Resume Nivolumab Combined with Fluorouracil and Cisplatin (Arm B)**

Subjects in Arm B may resume dosing only when criteria for BOTH resumption of nivolumab ([Section 4.5.4.1](#)) AND chemotherapy ([Section 4.5.4.2](#)) are met. That is, nivolumab and chemotherapy must be administered together until treatment discontinuation criteria ([Section 4.5.5](#)).

### **4.5.5 Treatment Discontinuation Criteria**

#### **4.5.5.1 Nivolumab and/or Ipilimumab Treatment Discontinuation (Arms A and B)**

Treatment should be permanently discontinued for the following:

- Any Grade 2 drug-related uveitis, eye pain or blurred vision that does not respond to topical therapy and does not improve to Grade 1 severity within the re-treatment period OR requires systemic treatment
- Any Grade  $\geq 2$  pneumonitis with or without a causal relationship to nivolumab and/or ipilimumab
- Any Grade 3 non-skin, drug-related adverse event lasting  $> 7$  days or recurs, with the following exceptions for laboratory abnormalities, diarrhea, colitis, neurologic toxicity, drug-related uveitis, pneumonitis, bronchospasm, hypersensitivity reactions, infusion reactions, and endocrinopathies:
  - Grade 3 drug-related diarrhea, colitis, neurologic toxicity, myocarditis, uveitis, bronchospasm, hypersensitivity reaction, or infusion reaction of any duration requires discontinuation
  - Grade 3 drug-related endocrinopathies adequately controlled with only physiologic hormone replacement do not require discontinuation
  - Grade 3 drug-related laboratory abnormalities do not require treatment discontinuation except:
    - ◆ Grade 3 drug-related thrombocytopenia  $> 7$  days or associated with bleeding requires discontinuation
    - ◆ Any drug-related liver function test (LFT) abnormality that meets the following criteria require discontinuation:
      - Grade  $\geq 3$  drug-related AST, ALT or Total Bilirubin requires discontinuation
      - Concurrent AST or ALT  $> 3 \times$  ULN and total bilirubin  $> 2 \times$  ULN
- Any Grade 4 drug-related AE or laboratory abnormality (including but not limited to creatinine, AST, ALT, or total bilirubin), except for the following events which do not require discontinuation:
  - Grade 4 neutropenia  $\leq 7$  days
  - Grade 4 lymphopenia or leukopenia
  - Isolated Grade 4 amylase or lipase abnormalities that are not associated with symptoms or clinical manifestations of pancreatitis.

- Isolated Grade 4 electrolyte imbalances/abnormalities that are not associated with clinical sequelae and are corrected with supplementation/appropriate management within 72 hours of their onset
- Any drug-related Grade 4 endocrinopathy and Grade 3 adrenal insufficiency requires discontinuation
- Any treatment delay resulting in an interruption in nivolumab dosing > 8 weeks, or interruption in ipilimumab > 12 weeks, with the following exceptions:
  - Dosing delays to allow for prolonged steroid tapers to manage drug-related AEs are allowed.
  - Dosing delays lasting >8 weeks for nivolumab and >12 weeks for ipilimumab from the previous dose that occur for non-drug-related reasons may be allowed if approved by the BMS medical monitor.

Prior to re-initiating treatment in a subject with a dosing delay lasting > 8 weeks, the BMS medical monitor must be consulted. Tumor assessments should continue as per protocol even if dosing is delayed. Periodic study visits to assess safety and laboratory studies should also continue every 6 weeks or more frequently if clinically indicated during such dosing delays.

Any AE, laboratory abnormality, or intercurrent illness which, in the judgment of the Investigator, presents a substantial clinical risk to the subject with continued nivolumab dosing.

The assessment for discontinuation of ipilimumab should be made separately from the assessment made for discontinuation of nivolumab. Although there is overlap among the discontinuation criteria, if discontinuation criteria are met for ipilimumab but not for nivolumab, treatment with nivolumab may continue if ipilimumab is discontinued.

In nivolumab plus ipilimumab combination treatment (Arm A), if a subject meets the criteria for discontinuation of ipilimumab but not nivolumab, treatment with nivolumab may not resume until the AE has fully resolved and the subject has discontinued steroids, if they were required for treatment of the AE. The relationship to ipilimumab should be well documented in the source documents. Nivolumab should be resumed at a dose of 3 mg/kg every 2 weeks.

If a subject meets the criteria for discontinuation of nivolumab but not for ipilimumab, both nivolumab and ipilimumab must be discontinued due to the lack of clinical efficacy of ipilimumab monotherapy (Section 1.1.6).

If a subject in the nivolumab and ipilimumab combination arm (Arm A) meets criteria for discontinuation and investigator is unable to determine whether the event is related to both or one study drug, the subject should discontinue both nivolumab and ipilimumab and be taken off the treatment phase of the study.

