### **1.4.3 Safety Summary**

Nivolumab has been studied in over 12,300 subjects and is widely approved in multiple indications. Extensive details on the safety profile of nivolumab are available in the IB, and will not be repeated herein.

Overall, the safety profile of nivolumab monotherapy as well as combination therapy is manageable and generally consistent across completed and ongoing clinical trials with no Maximum Tolerated Dose (MTD) reached at any dose tested up to 10 mg/kg. Most AEs were low-grade (Grade 1 to 2) with relatively few related high-grade (Grade 3 to 4) AEs. There was no pattern in the incidence, severity, or causality of AEs with respect to nivolumab dose level.

A pattern of immune-related AEs has been defined, for which management algorithms have been developed; these are provided in [Appendix 1](#). Most high-grade events were manageable with the use of corticosteroids or hormone replacement therapy (endocrinopathies) as instructed in these algorithms.

Additional details on the safety profiles of nivolumab and ipilimumab, including results from other clinical studies, are also available in the respective nivolumab and ipilimumab IBs.

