### **3.5 Discontinuation of Subjects following any Treatment with Study Drug**

Subjects MUST discontinue investigational product (and non-investigational product at the discretion of the investigator) for any of the following reasons:

- Subject's request to stop study treatment
- Any clinical AE, laboratory abnormality or intercurrent illness which, in the opinion of the investigator, indicates that continued participation in the study is not in the best interest of the subject
- Termination of the study by BMS
- Loss of ability to freely provide consent through imprisonment or involuntarily incarceration for treatment of either a psychiatric or physical (eg, infectious disease) illness. (Note: Under specific circumstances, a participant who has been imprisoned may be permitted to continue as a participant. Strict conditions apply and BMS approval is required.)
- Criteria listed in [Section 4.5.5](#)
- Disease progression as assessed by RECIST 1.1 criteria, unless the subject meets criteria for treatment beyond progression ([Section 4.5.6](#)).

In the case of pregnancy, the investigator must immediately notify the Sponsor or designee of this event. In most cases, the study drug will be permanently discontinued in an appropriate manner (eg, dose tapering if necessary for subject safety). Please contact the Sponsor or designee within 24 hours of awareness of the pregnancy. If the investigator determines a possible favorable benefit/risk ratio that warrants continuation of study drug, a discussion between the investigator and the Sponsor or designee must occur.

All subjects who discontinue study drug should comply with protocol specified follow-up procedures as outlined in [Section 5](#). The only exception to this requirement is when a subject withdraws consent for all study procedures including post-treatment study follow-up or loses the ability to consent freely (ie, is imprisoned or involuntarily incarcerated for the treatment of either a psychiatric or physical illness).

If study drug is discontinued prior to the subject's completion of the study, the reason for the discontinuation must be documented in the subject's medical records and entered on the appropriate case report form (CRF) page.

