## 4.5.2 Dose Delay Criteria

### 4.5.2.1 Dose Delay Criteria for Nivolumab and/or Ipilimumab (Arms A and B)

Nivolumab and/or ipilimumab administration should be delayed for the following:

- Any Grade  $\geq 2$  non-skin, drug-related AE, with the following exception:
  - Grade 2 drug-related fatigue does not require a treatment delay.
- Grade 2 drug-related creatinine,
- Any Grade  $\geq 3$  skin, drug-related AE
- Any Grade 3 drug-related laboratory abnormality, with the following exceptions for lymphopenia, AST, ALT, or total bilirubin and asymptomatic amylase or lipase abnormalities:
  - Grade 3 lymphopenia does not require dose delay
  - If a subject has a baseline AST, ALT, or total bilirubin that is within normal limits, delay dosing for drug-related Grade  $\geq 2$  toxicity
  - If a subject has baseline AST, ALT, or total bilirubin within the grade 1 toxicity range, delay dosing for drug-related Grade  $\geq 3$  toxicity
  - Any Grade  $\geq 3$  drug-related amylase or lipase abnormality that is not associated with symptoms or clinical manifestations of pancreatitis does not require dose delay.
- Any AE, laboratory abnormality, or intercurrent illness which, in the judgment of the investigator, warrants delaying the dose of study medication.

Subjects who have drug-related toxicities that meet the criteria for dose delay should have both drugs (ipilimumab and nivolumab) delayed until retreatment criteria are met (exceptions apply to the retreatment criteria after dose delay of ipilimumab and nivolumab for Grade  $\geq 3$  amylase and lipase abnormalities that are not associated with symptoms or clinical manifestations of pancreatitis and that are attributed to ipilimumab alone).

Subjects who require delay of nivolumab and ipilimumab should be re-evaluated weekly or more frequently if clinically indicated and resume nivolumab and/or ipilimumab dosing when re-treatment criteria are met.

Tumor assessments should continue as per protocol even if dosing is delayed. Periodic study visits to assess safety and laboratory studies should also continue every 6 weeks or more frequently if clinically indicated during such dosing delays.

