#### 4.5.4 Criteria to Resume Dosing

##### 4.5.4.1 Criteria to Resume Nivolumab or Ipilimumab (Arms A and B)

Subjects may resume treatment with study drug when the drug-related AE(s) resolve to Grade  $\leq 1$  or baseline value, with the following exceptions:

- Subjects may resume treatment in the presence of Grade 2 fatigue
- Subjects who have not experienced a Grade 3 drug-related skin AE may resume treatment in the presence of Grade 2 skin toxicity
- For subjects with Grade 2 AST, ALT, or total bilirubin elevations, dosing may resume when laboratory values return to baseline and management with corticosteroids, if needed, is complete.
- Subjects with combined Grade 2 AST/ALT AND total bilirubin values meeting discontinuation parameters (Section 4.5.5) should have treatment permanently discontinued.
- Drug-related pulmonary toxicity, diarrhea or colitis must have resolved to baseline before treatment is resumed. Subjects with persistent Grade 1 pneumonitis after completion of a steroid taper over at least 1 month may be eligible for retreatment if discussed with and approved by BMS Medical Monitor.
- Subjects with Grade < 4 drug-related endocrinopathies adequately controlled with only physiologic hormone replacement may resume treatment after consultation with the BMS Medical Monitor.

If dose delay is necessary, both nivolumab and ipilimumab must be delayed until treatment can resume. However, if a nivolumab-related infusion reaction prevents subsequent infusion of ipilimumab on the same day, the dose of ipilimumab should be replaced as soon as possible. In such instances, at least 37 days must elapse between the replacement dose of ipilimumab and the administration of the next dose of nivolumab combined with ipilimumab.

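### The restart rule for endocrinopathies (Protocol 4.5.4.1) does not exclude Grade 3 adrenal insufficiency, which Protocol 4.5.5.1 makes a permanent stop

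*Protocol*

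**What the plan says.** Four parts of the Protocol bear on this.

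- **Permanent stop (4.5.5.1).** Among the events for which nivolumab and/or ipilimumab must be stopped permanently: "Any drug-related Grade 4 endocrinopathy and Grade 3 adrenal insufficiency requires discontinuation". Whether the event is controlled makes no difference.
- **Sub-bullet in the same section (4.5.5.1).** Under the trigger for Grade 3 non-skin events that last more than 7 days or recur: "Grade 3 drug-related endocrinopathies adequately controlled with only physiologic hormone replacement do not require discontinuation". Adrenal insufficiency is not set apart.
- **Restart (4.5.4.1).** "Subjects with Grade < 4 drug-related endocrinopathies adequately controlled with only physiologic hormone replacement may resume treatment after consultation with the BMS Medical Monitor". Adrenal insufficiency is not set apart here either, and there is no pointer to 4.5.5.
- **General obligation (3.5).** "Subjects MUST discontinue investigational product (and non-investigational product at the discretion of the investigator) for any of the following reasons". The criteria in 4.5.5 are one of the reasons listed.

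Another bullet in the 4.5.4.1 list does refer to the stop section: "Subjects with combined Grade 2 AST/ALT AND total bilirubin values meeting discontinuation parameters (Section 4.5.5) should have treatment permanently discontinued".

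**The concern.** A subject with drug-related Grade 3 adrenal insufficiency, controlled on physiologic replacement, gets two different answers depending on which section the site opens. A site working through a dose delay would naturally go to the restart criteria. There it would find a bullet whose grade ceiling takes the subject in. After consulting the Medical Monitor it could re-dose someone whom the stop rule removes from treatment for good.

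Being controlled on replacement is not a remote condition. Section 1.4.3 says of immune-related events: "Most high-grade events were manageable with the use of corticosteroids or hormone replacement therapy (endocrinopathies) as instructed in these algorithms". Section 3.4.3 permits adrenal replacement steroids on study, so the concomitant-medication rules would not block a restart.

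What is at stake is the dosing safety of individual subjects in Arms A and B. The statistical design is not involved.

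**Working it through.** No figure in the plan needs reproducing. The check applies each rule to the same subject and then asks whether the restart rule can be reached.

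**Step 1: grades covered by each rule**

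| Event, drug-related and controlled on hormone replacement | Restart bullet, 4.5.4.1 | Stop line, 4.5.5.1 | Agree? |
|---|---|---|---|
| Endocrinopathy other than adrenal insufficiency, Grade 1–3 | may restart after consultation | not named | yes |
| Adrenal insufficiency, Grade 1–2 | may restart after consultation | not named | yes |
| Adrenal insufficiency, Grade 3 | may restart after consultation | permanent stop | **no** |
| Any endocrinopathy, Grade 4 | not covered | permanent stop | yes |

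The restart ceiling follows the Grade 4 half of the stop line and leaves out the adrenal half. The overlap is one grade of one event.

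**Step 2: does the restart list send the reader to the stop section?** The list in 4.5.4.1 has six bullets: fatigue; skin; Grade 2 AST, ALT or bilirubin; combined AST/ALT and bilirubin; pulmonary toxicity, diarrhea or colitis; endocrinopathies. One of the six, the combined AST/ALT and bilirubin bullet, cites 4.5.5. The endocrinopathy bullet does not.

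**Step 3: can the restart rule be reached?** Section 4.5.2.1 delays dosing for drug-related non-skin events of Grade 2 or higher, and tells sites to "resume nivolumab and/or ipilimumab dosing when re-treatment criteria are met". For Arm B, Section 4.5.4.3 says "Subjects in Arm B may resume dosing only when criteria for BOTH resumption of nivolumab" (citing 4.5.4.1) and of chemotherapy are met. Both nivolumab arms therefore come to this bullet.

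**Step 4: is 4.5.5.1 consistent with itself?** Read strictly, yes. The Grade 3 endocrinopathy sub-bullet is an exception only to the trigger about duration or recurrence, while the adrenal line is a separate criterion and sufficient alone under Section 3.5. But the sub-bullet comes first and the adrenal line only after the Grade 4 exceptions, so a site looking up a Grade 3 event could stop reading too soon.

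**Step 5: how strong is the gate?** The endocrinopathy bullet asks for consultation with the Medical Monitor. In the same list, retreatment with persistent Grade 1 pneumonitis needs the Medical Monitor's approval as well as discussion. The stated gate is therefore weaker for the adrenal case.

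**Step 6: who is under these rules?** 939 × 2/3 = 626 planned subjects in Arms A and B. This is the number to whom the rules apply. The documents give no rate of Grade 3 adrenal insufficiency from which to estimate how many would be affected.

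**The case against.** The strongest reply is that this is a missing reminder and not a conflict of rules. Section 3.5 is mandatory, the 4.5.5.1 list is permanent and more specific, and 4.5.4.1 only permits. On that structure the stop line prevails, and 4.5.4.1 applies only to delayed subjects who have met no stop criterion. Other restart criteria also leave out stop criteria. The pulmonary, diarrhea and colitis bullet carries no grade limit for restart after resolution to baseline, although pneumonitis of Grade 2 or higher and Grade 3 diarrhea or colitis are permanent stops. Section 4.5.4.3 does mention 4.5.5 for Arm B. An error would need both the site and the Medical Monitor to overlook the stop line.

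Much of this stands. The precedence is accepted, the consultation is a real safeguard, and Section 1.5 describes immune-mediated events with the Arm A regimen as mostly low grade. The endocrinopathy algorithm in Appendix 1 is a figure not available here, so it may or may not deal with adrenal events; Appendix 1 presents the algorithms as guidance.

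The reply does not remove the point. Bullets with no grade limit leave the reader to look for one elsewhere. This bullet states its own ceiling, and that ceiling admits the barred event. The precedence has to be inferred, because neither section states it. The mention of 4.5.5 in 4.5.4.3 is general and does nothing for Arm A.

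**Conclusion.** The concern holds. For controlled, drug-related Grade 3 adrenal insufficiency, the restart bullet in 4.5.4.1 as written gives an answer that 4.5.5.1 rules out. This is an internal inconsistency in a dosing-safety rule and should be corrected. The sponsor's safety position is not in dispute: the stop line is taken as the intended rule, on the strength of Section 3.5.

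The size is limited to one grade of one endocrinopathy, in the two nivolumab arms. Confidence is high for the comparison of texts. The practical frequency is unknown and may be low. No endpoint definition, significance level, event count or power figure depends on it.

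**What to change.** In 4.5.4.1, add to the endocrinopathy bullet an exception for Grade 3 adrenal insufficiency, stating that it requires permanent discontinuation and citing Section 4.5.5.1. Add the same exception to the Grade 3 endocrinopathy sub-bullet in 4.5.5.1. The second change is not needed for logical consistency, but it prevents the misreading described in Step 4.

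The cost is one clause at each of two bullets in the next protocol amendment, with no new procedure, data or patients.

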#### **4.5.5.2 Fluorouracil and Cisplatin Dose Discontinuation (Arms B and C)**

Except where specified below, both chemotherapy drugs in the fluorouracil and cisplatin combination regimen should be discontinued for any of the following (applies to Arms B and C):

- Any drug-related Grade 4 toxicity including laboratory abnormalities the subject will be discontinued from the relevant study drug, with the following exceptions:

- Isolated Grade 4 electrolyte abnormalities not associated with clinical sequelae and are adequately managed and corrected within 72 hours of onset
- Grade 4 neutropenia  $\leq 7$  days
- Grade 4 lymphopenia
- Any Grade 3 non-skin, drug-related adverse event lasting  $> 7$  days, with the following exceptions:
  - Grade 3 drug-related laboratory abnormalities do not require treatment discontinuation, except for the following scenarios:
    - ◆ Grade  $\geq 3$  drug-related thrombocytopenia associated with clinically significant bleeding requires discontinuation
    - ◆ Any drug-related liver function test (LFT) abnormality that meets the following criteria requires discontinuation:
      - AST or ALT  $> 8 \times$  ULN
      - Total bilirubin  $> 5 \times$  ULN
      - Concurrent AST or ALT  $> 3 \times$  ULN and total bilirubin  $> 2 \times$  ULN
        - ◆ Any cisplatin-related decrease in creatinine clearance to  $< 50$  mL/min (using the Cockcroft Gault formula or any chosen measured creatinine clearance method) requires discontinuation of cisplatin, unless corrected within  $\pm 7$  days of the scheduled dosing
  - Grade 3 lasting  $> 7$  days OR Grade 4 peripheral neuropathy
  - Any drug-related adverse event which recurs after two prior dose reductions for the same drug-related adverse event (as specified in [Section 4.5.3.2](#)) requires discontinuation of the drug(s) which was/were previously dose reduced.
  - Any Grade  $\geq 3$  drug-related hypersensitivity reaction or infusion reaction requires discontinuation of the drug(s) felt to be causing the reaction. The drug not felt to be related to the hypersensitivity reaction or infusion reaction may be continued.
  - Any event that leads to delay in dosing of any study drug(s) for  $> 8$  weeks from the previous dose requires discontinuation of that drug(s) with the following exception:
    - Dosing delays  $> 8$  weeks that occur for non-drug-related reasons may be allowed if approved by the BMS Medical Monitor. Prior to re-initiating treatment in a subject with a dosing delay lasting  $> 8$  weeks, the BMS Medical Monitor must be consulted. Tumor assessments should continue as per protocol even if dosing is delayed.
  - Any adverse event, laboratory abnormality, or intercurrent illness which, in the judgment of the Investigator, presents a substantial clinical risk to the subject with continued treatment.

Subjects could be discontinued from any or both of the study drugs on the FP regimen if, in the opinion of the investigator it is inappropriate to continue on the basis of safety or efficacy.

Subjects who discontinue one of the study drugs on the FP regimen may at the investigators discretion continue administration of the other study drugs. For example, if Cisplatin is discontinued, 5FU may be continued at the intended dose and schedule.

For subjects in Arm B, if the investigator is unable to determine whether an adverse event is due to nivolumab or to fluorouracil and cisplatin combination, then all drugs must be discontinued.

The assessments for discontinuation of chemotherapy and/or nivolumab in Arm B should be made separately. It is allowed to continue nivolumab alone when chemotherapy has been discontinued. Chemotherapy doublet or single drug is allowed to continue if nivolumab met its discontinuation criteria.

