#### **4.5.3.2.1 Fluorouracil and Cisplatin - Dose Reductions for Hematologic Toxicity**

Dose modifications for hematologic toxicities (according to CTCAE version 4) are summarized in Table 4.5.3.2.1-1. Dose adjustments are based on nadir blood counts (assessed as per local standards) since the preceding drug administration. Dose level adjustments for fluorouracil and cisplatin combination are relative to that of the preceding administration. Generally, both chemotherapy agents in the fluorouracil and cisplatin combination regimen should be dose reduced together for hematologic toxicity. After the first cycle, G-CSF may be used to assist hematologic recovery. Use local standards of care in the use of these supportive measures. Additionally, prophylactic antibiotics may be used according to local standards of care. Please report any antibiotic or growth factor use on the eCRF.

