**Table 4.5.3.2.1-1: Dose Modifications for Hematologic Toxicity (Arms B and C)**

Toxicity a	Fluorouracil	Cisplatin
Neutrophils (ANC) < 500/mm  lasting ≥ 5 days	Reduce one dose level	Reduce one dose level
Febrile neutropenia (body temperature ≥ 38.5°C and ANC < 1,000/mm  )	Reduce one dose level	Reduce one dose level
Platelet < 25,000/mm 	Reduce one dose level	Reduce one dose level
Platelets < 50,000/mm  with significant bleeding or requiring blood transfusion	Reduce one dose level	Reduce one dose level
Grade 4 hemoglobin (< 6.5 g/100 mL)	Reduce one dose level	Reduce one dose level

a If considered in the best interest of the subject, and consistent with local practice, investigators may decide to use supportive measures/treatment, and/or secondary prophylaxis instead of dose reductions for the next cycle. Also, if toxicity can clearly be attributed to one of the drugs, the investigator may choose to only dose reduce one of the cytotoxic agents.

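### Table 4.5.3.2.1-1 lowers the chemotherapy dose for Grade 4 hemoglobin, but Protocol 4.5.5.2 stops the relevant drug if the event is drug-related; the bleeding-platelet row overlaps in part

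*Protocol*

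**What the plan says.** Protocol Table 4.5.3.2.1-1 sets chemotherapy dose changes for hematologic toxicity in Arms B and C. All five rows take both drugs down one level. Two rows matter here: "Grade 4 hemoglobin (< 6.5 g/100 mL", and platelets below 50,000/mm³ "with significant bleeding or requiring blood transfusion".

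Footnote a loosens this in two ways. First, "investigators may decide to use supportive measures/treatment, and/or secondary prophylaxis instead of dose reductions for the next cycle". Second, where the toxicity is clearly due to one drug, "the investigator may choose to only dose reduce one of the cytotoxic agents". The lead-in (4.5.3.2.1) says "Dose adjustments are based on nadir blood counts", sets no attribution condition, and adds: "Generally, both chemotherapy agents in the fluorouracil and cisplatin combination regimen should be dose reduced together". It does not mention the discontinuation section.

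Protocol 4.5.5.2 covers the same two arms. Its opening line stops both chemotherapy drugs unless an item says otherwise. The Grade 4 item does say otherwise: "Any drug-related Grade 4 toxicity including laboratory abnormalities the subject will be discontinued from the relevant study drug, with the following exceptions". Three exceptions follow: isolated electrolyte abnormalities corrected within 72 hours, neutropenia of 7 days or less, and lymphopenia. A separate line requires discontinuation for drug-related thrombocytopenia of Grade 3 or higher with clinically significant bleeding. It is printed beneath the item on Grade 3 events lasting more than 7 days.

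Section 3.5 gives these criteria their force: "Subjects MUST discontinue investigational product (and non-investigational product at the discretion of the investigator) for any of the following reasons". The list that follows includes the criteria in 4.5.5.

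**The concern.** A site handling a severe hematologic event will naturally go to the table built for it. The route there is direct. Section 4.5.4.2 lets a subject restart once other drug-related toxicity is back to baseline or Grade 1, then sends the site to 4.5.3.2 for the dose. It names 4.5.5.2 only for combined liver-test values.

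On that route, a subject with drug-related Grade 4 anemia could be re-dosed with a drug that 4.5.5.2 says to stop. The same could happen after some cases of drug-related thrombocytopenia with bleeding. Sites reading different sections would treat the same event differently. The SAP would then count it as a dose reduction (7.4.2.4) at one site and as a discontinuation (7.6.3) at another.

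**Working it through.** This is a comparison of two printed rules. The only arithmetic is on the dose ladder.

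**1. Hemoglobin.** The table itself labels the event Grade 4, so no outside grading source is needed.

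| | Table 4.5.3.2.1-1 | Section 4.5.5.2 |
|---|---|---|
| Trigger | Grade 4 hemoglobin, any cause | Any drug-related Grade 4 toxicity, laboratory values included |
| Action | Both drugs down one level; footnote a allows less | Relevant drug stopped |
| Exceptions covering hemoglobin | not applicable | 0 of 3 |

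A drug-related case satisfies both triggers, and the actions cannot both be followed for the relevant drug. A case not attributed to chemotherapy satisfies only the table, so there is no conflict.

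**2. Dose after one drug-related event at the starting dose** (fluorouracil/cisplatin, mg/m²; levels from Table 4.5.3.2-1):

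- Table row: 800 × 0.75 = 600 and 80 × 0.75 = 60, so 600/60.
- Footnote a: 800/80 with supportive care; 800/60 or 600/80 if one drug is blamed.
- Section 4.5.5.2: 800/0 or 0/80 if one drug is the relevant one and the investigator continues the other at its intended dose, as the section permits; 0/0 if both are relevant.

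**3. Repeated events.** The ladder runs 800/80, then 600/60 (event 1), 400/40 (event 2), discontinue (event 3). Section 4.5.5.2 stops the relevant drug at event 1. The difference is 3 − 1 = 2 reduced-dose resumptions that 4.5.5.2 does not allow, and more if footnote a replaces a reduction.

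**4. Platelets with bleeding.** The table reduces both drugs one level below 50,000/mm³ with significant bleeding. The bleeding line in 4.5.5.2 names no single drug, so its opening line applies and both drugs stop. The overlap is partial for three reasons:

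- The stop rule needs Grade 3 or higher, and the documents print no CTCAE platelet cut-offs. If Grade 3 began at 50,000/mm³, every drug-related case in the row with clinically significant bleeding would meet the stop rule. If it began lower, only counts below that cut-off would. The row has no lower limit, so some overlap remains either way.
- The line sits under the item on events lasting more than 7 days but states no duration itself. If the limit carries over, the conflict is confined to longer events.
- The row also covers transfusion without bleeding, which the stop rule does not reach.

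**5. Cross-references.** The dosing sections 4.5.1.2 (Arm B) and 4.5.1.3 (Arm C) list delays, reductions, resumption and discontinuation (4.5.2 to 4.5.5) together. Section 4.5.4.3 refers Arm B to the discontinuation criteria. The lead-in to the non-hematologic table allows for discontinuation, and that table prints the instruction in some cells. The hematologic table and its lead-in do neither. None of these places says which action governs the two rows.

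**The case against.** The strongest reply is that the order is already settled. Section 3.5 makes the discontinuation criteria compulsory, both dosing sections tell the site to consult 4.5.5 alongside 4.5.3, and 4.5.5.2 refers back to 4.5.3.2 in its item on recurrent events. A careful site would stop the drug. On this view all that is missing is a reminder.

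Much of this stands. A reader might infer that the protocol gives no order of precedence, and that would be wrong. But the pointers send the site to both sections without reconciling the row. If 4.5.5.2 simply overrides it, the hemoglobin row is left mainly with anemia not attributed to chemotherapy, where a chemotherapy reduction has least purpose. The sponsor may have meant that, or may have overlooked an exception for anemia. The text does not say which.

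It is also fair to say that the two-resumption figure is a ceiling. It needs three drug-related Grade 4 anemias in one subject, with recovery each time. Failure to recover within 8 weeks of the last dose stops the causative drug anyway.

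Two wider readings are tempting and unsupported. One is that the whole platelet row contradicts 4.5.5.2; the limits above rule that out. The other is that the remaining three rows conflict too. They carry no printed grade, and the documents give no cut-offs with which to assign one.

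**Conclusion.** The hemoglobin conflict stands on the printed text, for drug-related events only. One of the table's five rows gives an action that 4.5.5.2 forbids for those events. A second row, platelets with bleeding, overlaps in part, to an extent that depends on unprinted CTCAE cut-offs and on whether the 7-day limit applies.

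Severity is minor. The consequence is confined to patient safety and consistent dosing across sites. The documents give no event rates, so the number of affected subjects is unknown. A reader might infer some effect on PFS, power or type I error; nothing in the documents supports that, since the conflict touches no sample size, event count or significance level.

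**What to change.** Three edits to the protocol:

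- Above Table 4.5.3.2.1-1, state that the reductions and the footnote a alternatives apply only when no discontinuation criterion in 4.5.5.2 is met.
- In the hemoglobin row, add: discontinue the relevant drug if drug-related. If the sponsor does intend re-dosing after Grade 4 anemia, add it to the Grade 4 exceptions in 4.5.5.2 instead.
- In the platelet row, add: discontinue both chemotherapy drugs per 4.5.5.2 if drug-related, Grade 3 or higher, and with clinically significant bleeding. Wording this row as the relevant drug only would create a new mismatch, because that term belongs to the Grade 4 item.

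The cost is one sentence and two row edits, by administrative letter or in the next amendment. No new data or procedures are needed.
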